## **2.3. RESEARCH HYPOTHESES OR ASSUMPTIONS**

1. Teachers who participate in a Child Mental Health Literacy program are able to significantly improve their knowledge regarding the identification of these problems and the delivery of first aids.
2. The establishments that participate in this training program significantly improve the detection rate of children with mental health problems.
3. The relevance of the diagnosis made by teachers when referring children with mental health problems to the corresponding CESFAM is greater than 80%.
4. The health-education networks where an intervention is carried out to articulate the referral of girls and girls with mental health problems, reduce the waiting time that goes between the referral and the first health care.

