### **2.4.2. SPECIFIC OBJECTIVES**

1. Build in a participatory way the contents of a literacy program in Child Mental Health (CMH) with teachers of Public Educational Establishments (PS) and key actors, from the commune of Valparaíso.
2. Implement the strategy of articulation in a network of CMH (ECO-Neighborhood Network) between schools, Primary and Secondary Health Care, Municipality, collaborating agencies of SENAME and other relevant programs in 2 territories of the commune of Valparaíso.
3. To evaluate whether the Child Mental Health Literacy program, aimed at teachers in public educational establishments, manages to significantly improve their knowledge in this regard.
4. To assess whether teachers participating in the CMH Literacy program significantly improve the detection rate of these problems among their pupils.
5. To evaluate whether the relevance of the research for referral from educational establishments to the corresponding CESFAM is greater than 80%.
6. To evaluate whether the health-education articulation strategy (ECO-Barrio Network) significantly improves waiting times between referral and the first care received by a child with a possible mental health problem.
7. Evaluate indicators of feasibility of the multicomponent intervention, which are useful for a future escalation (interest of teachers to participate, retention in the intervention, degree of satisfaction of all participants, facilitators and perceived barriers).

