3. The third part (months 12 to 24) consists of carrying out a pilot test taking 4 educational establishments located in two different territories of the commune of Valparaíso, in which the intervention will be carried out, and its results will be compared with 4 other equivalent educational establishments, from those same territories, which serve as control. Pre- and post-intervention assessments will be carried out, using a children's mental health knowledge survey, while referrals from facilities to the corresponding CESFAM will be recorded. Results will be compared between intervention and control results. Information is also collected to assess the participation of teachers in the intervention (feasibility analysis).

At the end of the intervention in the establishments that were the object of it, the quantitative indicators and results that were collected will be synthesized, and a qualitative analysis will be carried out (DEXPLIS design), based on discussion groups that involve the interested parties (teachers, mental health professionals and managers of both sectors). in which the results and achievements will be analyzed, barriers and facilitators of the process will be established, all of which will allow to complete the evaluation in a participatory way and to improve the components of the intervention, based on the empirical experience carried out.

After the end of the intervention, the intervention will also be carried out in its two components (teachers and health-education network) in the 4 establishments that served as control. In this way, an ethical requirement of not depriving the rest of the participants of a beneficial intervention is met. (Months 18 to 24)

Indicators, instruments and analysis procedures. For the detailed description of this point, the effectiveness analysis and the feasibility analysis of the pilot intervention are separated.

1) Evaluation of the effectiveness of the intervention. The effectiveness evaluation is based on comparing the following indicators between intervention and control establishments.

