- a) Level of knowledge of the teachers, using an *ad hoc* questionnaire, which is built in the phase prior to the intervention and validated by this team (which incorporates teachers). The conceptual framework of literacy in child and adolescent mental health will be used. This questionnaire will include all the aspects that are part of the training program aimed at teachers and will allow them to obtain scores for their different modules or dimensions. A test and semantic adaptation will be carried out with teachers from establishments in other sectors of the commune, which do not participate in the project, prior to its use within the project. It is expected that in the initial assessment (baseline), the results will be similar in the teachers of the intervention and control establishments. At the end of the intervention it is expected that scores have improved significantly in intervention facilities and have not changed in control facilities.
- b) Rates of referral of mental health problems in children. In each project establishment (intervention and control) a centralized register will be kept of the children indicated by their teachers who require mental health care during the intervention. This will also allow for centralized coordination for referral to the relevant CESFAM. In this way the detection rate can be calculated.
- c) Waiting time between referral from the educational establishment to professional care at the corresponding CESFAM. This indicator is obtained from the centralized register in each educational establishment, which includes the date on which it coordinated with CESFAM for its attention, and the registration of the first attention in the latter. The time elapsed between the two is the waiting time that will be used as an indicator.
- d) Rate of accuracy for referral of children with suspected psychiatric disorders from the school to health care. Each “case” referral will apply the Strength and Difficulties Questionnaire (SDQ). 25 items (scale 0-2).

2) Evaluation of the feasibility of the intervention. Feasibility assessment uses a combination of quantitative (indicator) and qualitative methods, which are described below.

- a) Level of interest of teachers in the intervention: It is estimated through the percentage of teachers who agree to start the training course, out of the total number of teachers who were invited (which would be the totality of each educational establishment).

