### 3.3. WORK PLAN

Specific Objective	Activity	Months																							
		1	2	3	4	5	6	7	8	9	10	11	12	13	14	15	16	17	18	19	20	21	22	23	24
1-Build in a participatory way the contents of a Literacy program in CMH	1-Presentation of the Ethics Committee Project	x																							
	2- Random selection of the 4 PS		x																						
	3-Contact and invitation to working meetings of key informants of the territories and PS		x	x																					
	4- Establish work teams in each selected PS			x																					
	6- Participatory design of the literacy program			x	x	x	x																		
2. Implement the ECO-Barrio network strategy	1- Contact with key agents of the CMH network	x																							
	2-Form a committee in each sector with the representatives of the institutions of the intersectoral ecosystem in CMH	x																							
	3- Develop a participatory work plan with objectives, goals, activities, deadlines and managers.		x	x	x																				
	4-Bimonthly work and follow-up meetings.			x	x	x	x	x	x	x	x	x	x	x	x	x	x	x	x						
3. Assess whether the literacy program significantly improves knowledge in CMH	1- Recruitment of teachers to participate in the literacy intervention.			x	x	x	x																		
	2- Development of knowledge instrument in CMH			x																					
	3-Test of application of the instrument in PS of non-intervened sectors.				x																				
	4-Semantic adaptation of the instrument.					x																			
	5-Implementation of online literacy course (G1 and G2)							x	x	x	x	x	x	x	x	x	x	x	x						
	6 Evaluation of teachers intervened with instrument (pre and post intervention)							x					x							x					
4- Evaluate if the detection rate of CMH problems is significantly improved	1-Random selection of 2 PS similar to those selected in a neighborhood where the intervention has not been implemented				x																				
	2- Determine the detection rate in schools that received the literacy program compared to control schools												x										x		
5.Evaluate whether the relevance of referral to	1- Determine how many of the referred children enter Mental Health treatment (regardless of the device or level of complexity)						x	x	x	x	x	x	x	x	x	x	x	x	x						

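### Referral relevance is tested against 80% with two unreconciled measures, and one of them, entry into treatment, depends on the wait and has no stated follow-up per child

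*Combined protocol and SAP*

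**What the plan says.** Hypothesis 3 (section 2.3) sets the criterion: "The relevance of the diagnosis made by teachers when referring children with mental health problems to the corresponding CESFAM is greater than 80" per cent. Specific objective 5 (section 2.4.2) repeats it: "To evaluate whether the relevance of the research for referral from educational establishments to the corresponding CESFAM is greater than 80" per cent. Two places describe how the quantity is measured.

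- **Work plan (section 3.3), objective 5, activity 1:** "Determine how many of the referred children enter Mental Health treatment (regardless of the device or level of complexity". The row carries 13 marks, in months 6 to 18.
- **Section 3.1, effectiveness indicator d:** "Rate of accuracy for referral of children with suspected psychiatric disorders from the school to health care". The method given is that each case "referral will apply the Strength and Difficulties Questionnaire (SDQ). 25 items (scale 0-2". No cut-off, respondent or time of completion is stated.

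The timing comes from three places. Indicator b in section 3.1 says that "a centralized register will be kept of the children indicated by their teachers who require mental health care during the intervention", with no closing date for referrals. The work plan row "5-Implementation of online literacy course (G1 and G2" is marked in months 7 to 18. The fieldwork text in section 3.1 gives another calendar: "The third part (months 12 to 24) consists of carrying out a pilot test taking 4 educational establishments".

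The wait from referral to first care is a separate outcome (indicator c, hypothesis 4, objective 6). No baseline or expected value is given for it.

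**The concern.** A fixed threshold needs one definition of what is compared with it. Here the same hypothesis could pass on the SDQ and fail on treatment entry, or the reverse, and the plan does not say which result counts.

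The two measures also answer different questions. An SDQ completed at referral bears on whether the teacher picked out a child with difficulties. Entry into treatment requires, in addition, that a service has a place and that enough time has passed. The protocol's own problem statement lists waiting lists among the barriers, and reports that only 41.6% of children and adolescents with a disabling psychiatric disorder had consulted any service in the previous year. Objective 6 sets out to change the wait. If the network shortens it, relevance measured by treatment entry can rise with no change in teachers' judgement. If the wait stays long, accurate teachers can look inaccurate. The pilot is meant to inform a larger study, which would inherit that ambiguity.

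**Working it through.** **Plan's own figure.** The 80% is a set threshold. The documents give no sample size, delay or follow-up calculation behind it, so there is nothing to reproduce.

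**Inputs from the documents.** Threshold 0.80. Treatment-entry row in months 6 to 18, so T = 13 months. Course row in months 7 to 18, so T = 12. Section 3.1 starts the pilot at month 12 and moves on to the control schools from month 18, so T = 18 − 12 = 6.

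**Assumptions not in the documents.** Every referral is correct and every child eventually enters treatment after a delay d. Referrals accrue over T months. Entry is read only to the end of month 18.

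**Step 1: even referrals, fixed delay.** Only children referred at least d months before the close are seen to enter, so the observed proportion is (T − d)/T. It falls below 0.80 when d > 0.2T.

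- T = 13: 0.2 × 13 = 2.6 months
- T = 12: 0.2 × 12 = 2.4 months
- T = 6: 0.2 × 6 = 1.2 months

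At d = 3 the observed proportion is 10/13 = 76.9% or 9/12 = 75.0%.

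**Step 2: variable delay.** With exponential delays of mean m, the observed proportion is 1 − (m/T)(1 − exp(−T/m)). It reaches 0.80 at m = 2.62 (T = 13) or 2.42 (T = 12), so the shape of the delay matters little here.

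**Step 3: uneven referrals.**

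- Rising linearly: proportion ((T − d)/T)², limit T(1 − √0.8) = 1.37 (T = 13) or 1.27 (T = 12) months.
- Falling linearly: proportion 1 − (d/T)², limit T√0.2 = 5.81 (T = 13) or 5.37 (T = 12) months.

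**Step 4: tracking beyond the last referral.** With F further months, the fixed-delay limit is F + 0.2T. If the first group's referrals fall in months 7 to 12 and are tracked to month 18, then T = 6, F = 6 and the limit is 6 + 1.2 = 7.2 months.

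**Step 5: less than perfect accuracy.** With true relevance 90%, the limit solves 0.9(1 − d/T) = 0.8, so d = T(1 − 0.8/0.9) = 1.44 (T = 13) or 1.33 (T = 12) months.

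**Result.** For fully accurate referrals, the delay at which the observed figure crosses 80% runs from about 1.2 to 7.2 months over these scenarios. That range illustrates the sensitivity and is not a bound: a six-month window with rising referrals gives 6 × (1 − √0.8) = 0.63 months.

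**The case against.** The strongest reply is that the cut-off is read into calendar marks. A reader might infer that there is no follow-up after the last referrals, that a child still queuing at month 18 is scored as an irrelevant referral, and that month-6 referrals by teachers not yet trained are pooled in. None of this is written. The register is tied to the intervention period, with no closing date. The same work plan reads the detection rate at months 12 and 22, so work on the referral data continues past month 18. In the copy reviewed, the table also breaks off at the objective 5 row, with its label cut short and no rows for objectives 6 and 7, so a later step may simply not be visible. These points stand, and the month-18 arithmetic is therefore conditional.

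It can also be said that the work plan is only a calendar and that indicator d governs. The documents do not say so, and indicator d as written cannot yield a rate because it has no cut-off. Nor is the SDQ beyond question: completed by the referring teacher alone, it would not be independent of the referral it is meant to check.

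Finally, the study is sized on the detection rate, and relevance is a benchmark within a pilot. That limits the severity. It does not remove the need to say what is compared with 80%.

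**Conclusion.** The documents establish three things. One 80% criterion has two unreconciled measures. Treatment entry confounds referral accuracy with access and with an outcome that the intervention is designed to move. No follow-up per referred child is stated. None of these depends on the month-18 inference.

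The size is conditional. With even referrals over 12 to 13 months and entry read only to month 18, fully accurate referrals would fall below 80% at a delay above 2.4 to 2.6 months. Under the other patterns and windows examined, the limit lies between about 1.2 and 7.2 months. A reader might go further and conclude that the programme will miss 80% because of the queue. The documents give no waiting time, so they do not support that. What they show is that the result depends on timing rules left open. This should be fixed; it does not invalidate the design.

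**What to change.** 1. Reconcile indicator d in section 3.1 with the objective 5 row of the work plan, and name one measure for the 80% test. The SDQ is the natural choice because it is already planned for each referred case. State one cut-off and the respondent in advance, preferably not the referring teacher alone. Define relevance as referred children with a positive SDQ divided by referred children with a completed SDQ, and report how many lack one.
2. Count referrals made after each group's teachers start the course. Report pre-course referrals separately.
3. Settle which calendar applies (course in months 7 to 18, or pilot in months 12 to 24), since it fixes the referral window.
4. Keep treatment entry as a secondary process indicator with the same follow-up for every child. Either report entry within a fixed time of referral, counting only children who can complete that time, or estimate time to entry with children still waiting treated as censored. Children assessed and not taken into treatment should count as not entering, rather than as censored. Existing records up to month 24 can be used. If referrals run for 12 months to month 18, six more months of tracking raise the fixed-delay limit from 2.4 to 6 + 2.4 = 8.4 months.

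The cost is wording in the protocol and work plan, a few more months of record look-up, and fewer referrals in the 80% test. A respondent other than the teacher may add some collection effort.

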#### **4. RESULTS, IMPLEMENTATION AND DISSEMINATION**

##### **4.1. IMPLEMENTATION OF EXPECTED PRODUCT(S)**

###### **4.1.1. EXPECTED RESULTS AND/OR OUTPUTS**

Result/Product Name	Enter a brief description of the result/product
1) Child and Youth Mental Health Literacy Program for teachers on an e-learning platform	Free literacy program in Child and Adolescent Mental Health based on videotaped educational capsules, feasible to be modified according to contextual and local needs.
2). Technical recommendations to implement a territorial Child and Adolescent Mental Health Network	Implementation Manual of "Red-Eco Barrio" with description of the methodology used, facilitators, obstacles and indicators obtained
3) 2 scientific publications in indexed journals (WOS or SCOPUS).	2 scientific publications will be made: the first with a description of the multicomponent intervention and its participatory construction, and the second with the results of effectiveness and feasibility.
4) Presentations at scientific congresses in the field of child mental health	There will be 2 presentations at scientific congresses, as posters or free communication, related to specific products: the child mental health literacy program for teachers and the articulation of the local network (Eco Barrio program)

###### **4.1.2. IMPLEMENTATION OF THE EXPECTED PRODUCT(S)**

The direct beneficiaries will be PS teachers from the commune of Valparaíso who receive basic education students and who voluntarily agree to participate in the child mental health literacy program. To this end, an e-learning platform will be developed with audiovisual resources for training in CMH, asynchronously, in addition to contemplating some synchronous meetings to resolve doubts with the participants of the training.

Additionally, training activities and facilitation of intersectoral coordination will be programmed for health, education, SENAME and other relevant actors, in order to support the process of identifying students who require mental health care in an opportune and pertinent manner, through the eco-neighborhood network that will be implemented in 2 sectors of Valparaíso. those that will be carried out online, given the current global health context, and taking advantage of the familiarity that has been given with these means that facilitate the meetings and reduce the expenditure of resources for their participants.

In relation to the e-learning platform, the project will remain as an input for CORMUVAL and the ECO-Barrio Network, so that they can continue using it in their activities.

Finally, the development of a critical nucleus and associativity of the University of Valparaíso with specialized groups is expected, which promotes more research in this area and constitutes updated and complementary information to what is currently available, in addition to contributing to the technological development of science solutions applied to public health in the area of child mental health. These expert groups have been described throughout the project.

#### **4.2. DISSEMINATION ACTIVITIES**

During the years of execution of the Project, it is expected that members of the team of researchers will attend national and international congresses specialized in child psychiatry that will allow the presentation of the partial and final results of the present research project on literacy in mental health. The first year is planned to participate in the congress of the Chilean society of psychiatry and child neurology, as well as the second year, a period in which the congress or international congress of the American Society of Child Psychiatry will also be attended.

In turn, the results of this research will provide evidence that will be published in scientific journals. It is planned to publish at least two collaborative articles in indexed journals (WOS or SCOPUS).

Additionally, during the first and second year of project execution, it is planned to hold two online dissemination seminars for the city of Valparaíso. The aim of these seminars will be to present the preliminary results of the study to the local community (mental health professionals, public school teachers, educational community, Sename professionals, primary health professionals).

At the end of the second year, a closing event is planned. A training activity will be carried out aimed at professionals, academics and students of health and social sciences careers with the aim of presenting and training in the relevance of the implementation of a digital literacy strategy in mental health for key actors of the intersectoral ecology of children in school, in order to positively influence their mental health and thereby in the generation of well-treated environments and communities that contribute to their integral development. In addition, to relieve the work in intersectoral mental health networks, in order to develop an articulation device that we have called "ECO-Neighborhood Network", which serves as a support for the implementation of the knowledge acquired by teachers, one of its purposes being to impact on the early and pertinent investigation of mental health disorders that require to be attended in mental health programs of both the primary health network and the secondary.

#### **5.4. ASSOCIATIVITY**

The University of Valparaíso is the main beneficiary institution of this research project, and the associated institution is the Salvador de Valparaíso Psychiatric Hospital, which for more than 50 years has constituted its main clinical field in Psychiatry and Mental Health. This will allow a strong commitment and teaching-care associativity, through the incorporation of thesis students and residents of Child Psychiatry. Additionally, the incorporation of the

This will allow the collaboration between different Academic Units, which will allow the contribution of undergraduate and postgraduate students of Medicine, the professionals of the Mental Health teams of the CESFAM, as promised by the Director of the Municipal Corporation of Education in his letter of commitment.

On the other hand, this project has the commitment of the Executive Director of the Local Public Education Service of Valparaíso, who will facilitate the participation of those teachers of the teaching staff of the public schools of Valparaíso who wish to participate (respecting the autonomy of the teachers). In addition, this service undertook to hold periodic assemblies with key actors in its community and the research team, to provide feedback on the relevance of the activities implemented in the school and community environment.

On the other hand, from the academic point of view, the researchers involved have a permanent collaboration relationship with teams from the University of Chile, McMaster University, University of Maryland, Autonomous University of Barcelona and Harvard Medical School. This will contribute to associativity in terms of information sharing, dissemination activities and generation of manuscripts of the knowledge generated.

